2.8 Rationale for Correlative Studies Background: Microbiome and blood sample collection

Patients accrued to the study will donate a stool specimen and a blood sample both before and after radiation, to study their changes in the microbiome and circulating immune correlates during and after radiotherapy, and at 3-6 month follow up.

Preliminary results from our ongoing study “Effect of Radiotherapy Variables on Circulating Effectors of Immnue Response and Local Microbiome” PI: [name], IRB Protocol #: 1708018471 demonstrate depletion of circulating lymphocytes in prostate cancer patients undergoing protracted standard radiation compared to 5-fraction SBRT (which is the regimen we will use on this study) (results submitted to ASTRO). We will study this phenomenon further in patients undergoing SBRT on this study. We have also found a temporary increase in neutrophil:lymphocyte ratio (NLR) during radiation to the prostate in our dataset of patients; patients enrolled on this protocol will also have assessment of NLR at baseline, after RT and at 3-month follow up.

The host microbiome is an emerging topic of investigation, with growing evidence that commensal microbiota impacts anti-tumor immune response, and sensitivity to systemic therapies and immunotherapy. Commensal bacteria outnumber human cells by at least 10-fold, colonizing host mucosal surfaces and playing critical roles in metabolism, defense against pathogens, and crosstalk between the environment and immune system. Preclinical studies suggest that microbiota impact the immune system through a number of mechanisms, including possible modulation of myeloid-derived cells; stimulation of T helper cells, and enhancement of memory T-cell response. Dysbiosis, or shifts in microbial composition, may modulate response to cancer therapy. We hypothesize that the underlying microbial community composition will be impacted by administration of radiation to the prostate. Our preliminary data in mice suggests fluctuations in composition, abundance and diversity after local tumor-directed radiation. We hope to explore this further in patients who are undergoing SBRT by collecting microbiome samples at baseline, upon completion of RT, and at follow up.

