5 STUDY PROCEDURES

	Pre-Study	Fx 1	Fx2	Fx 3	Fx 4	Fx 5*	Post-RT Visits (3-6 months, 9- 12 months s/p RT)
Informed consent	X						
Demographics	X						
PSA	X						X
Acute/Late Toxicity Assessment (CTCAE)	X					X	X
EPIC-26, I-PSS	X						X
Imaging: Planning CT/MR;	X						
Blood draw and microbiome sample	X					X	X**

** no blood draw at 9-12 months.

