9 CORRELATIVE/SPECIAL STUDIES

9.1 Correlative Study: Blood draws for immune correlates and microbiome collection

Patients will provide blood draw prior to, at the completion of radiation and at 3-6 months post treatment follow up. They will also be providing a stool sample for microbiome analysis at baseline, end of completion and 3-6 month follow up (last stool sample is optional). This is a correlative study.

Blood Sample Collection and Procedure

Blood samples (40-ml) will be collected in heparinized “Green Top” tubes (for PBMC and plasma isolation) and processed within 4 h of sample receipt. The PBMC will be isolated using a 1.077 g/ml Ficoll layer to enrich the leukocytes and remove the dead cells and any red cells, and cryopreserved in 10% DMSO, 90% human AB serum at 10×10^6

cells/vial and stored in liquid nitrogen for batch analysis. Plasma will also be aliquoted and stored at -80°C for batch analysis. We anticipate analyses of T cell subsets and neutrophil/lymphocyte ratios, as well as cytokine measurement and proliferation analyses (all markers of peripheral immune correlates to assess status over time).

Microbiome collection

Collection of Specimen(s): Patients will be provided with a stool collection container and be instructed on providing a specimen appropriately, which can be done from home or in the clinic.

Handling of Specimens(s): Samples received will be promptly frozen at 20 degrees C, and transferred within the next week to a -80 degree freezer or liquid nitrogen for long-term storage. DNA extractions and 16sRNA analysis will be performed once all samples are collected.

The microbial DNA will be isolated and used to provide DNA sequence information. We will perform taxonomic characterization of bacteria (using 16S rRNA). Prokaryotic diversity will be screened using massively parallel DNA sequencing, exploiting a multiplexing technique to generate 16S rRNA sequence tags, followed by analyses (statistical, clustering, and phylogenetic) to estimate the distribution of phylotypes, differential abundance, and the relative contributions between phylotypes and community dissimilarities to the overall diversity in individuals.

We will examine whether there are metagenome sequence content changes during radiation treatment, and study whether differences in gene content indicate differences in functional pathways between the normal and irradiated microbiome using pathway analysis.

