Statistical analysis of microbiome and metagenome composition will be performed in the R statistical programming environment using package *phyloseq*, which incorporates and builds upon community ecology packages such as *ade4* and *vegan* and employs the flexible graphic system *ggplot2*, to easily visualize complex data relationships. For 16S data, we will evaluate the adequacy of sequencing efforts using rarefaction plots. Alpha diversity index for each will be characterized through dominance, equitability, richness, evenness. The diversity metrics will be calculated at OTU and higher taxonomical levels to best characterize the community structure. We will test for associations of each of these alpha diversity metrics with the time relative to radiation exposure, using one-way ANOVA after even-sampling the observations to a depth cut-off maximizing the number of samples and depth. In addition, rank-abundance plots will be used to visualize differences in abundance of dominant taxa in the clinical and phenotypic groups. We will utilize skyline plots to visualize the patterns of community structure in terms of relative abundances in the collected samples between before and after the radiation treatment. Similarly, for metagenomic data, skyline plots will be used to reveal functional compositions of the samples. Heat-maps will be plotted to visualize clustering patterns in the data.

We will study the evolution of microbiome over time as a consequence of the radiation treatment. The relative abundances at each taxonomical level will be first normalized by log-ratio transformation. Then the transformed relative abundance of each individual taxa at multiple time points will be fitted by the linear mixed model along with the time effect and all subject-specific characteristics as the independent covariates. For the nonlinear trend, we will combine the nature splines with linear mixed model in the data analysis. The same model will be applied on the indices calculated in the ecology microbial analysis.

CBC collection

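### Section 12.3 lists two analyses of alpha diversity over time without saying which governs, and one of them, a one-way ANOVA, ignores that the stool samples are repeated on the same patients.

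*Combined protocol and SAP*

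**What the plan says.** The microbiome paragraphs of Section 12.3 contain two analyses that bear on alpha diversity over time.

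- **One-way ANOVA.** "We will test for associations of each of these alpha diversity metrics with the time relative to radiation exposure, using one-way ANOVA after even-sampling". No patient, block or repeated-measures term is named.
- **Linear mixed model.** The log-ratio-transformed abundance of each taxon is to be "fitted by the linear mixed model along with the time effect and all subject-specific characteristics as the independent covariates". The plan then adds: "For the nonlinear trend, we will combine the nature splines with linear mixed model in the data analysis". It closes with: "The same model will be applied on the indices calculated in the ecology microbial analysis". The alpha diversity metrics are the most natural meaning of those indices, although they are not named in that sentence.

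The sampling is serial. Section 2.8 describes "collecting microbiome samples at baseline, upon completion of RT, and at follow up", and Section 9.1 states: "They will also be providing a stool sample for microbiome analysis at baseline, end of completion and 3-6 month follow up". Section 9.1 makes the last sample optional.

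Section 12.1.3 calls the microbiome work exploratory. Section 12.2 plans 20 patients, and the Protocol Summary gives an accrual ceiling of 25.

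**The concern.** Time relative to radiation is a within-patient factor here: each patient contributes a sample at each visit. Ordinary one-way ANOVA treats the visits as independent groups. Stable differences between patients then stay in the residual, and the time effect is judged against too large an error.

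Hypothesis 3 in Section 1 predicts altered diversity from baseline to post-treatment to follow-up, which is a set of within-patient contrasts. If the ANOVA were taken as the answer, a null result could be reported as no change in diversity when the same samples, analysed within patient, would show one. Because the plan ranks neither analysis, the choice could also be made after both results are known.

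**Working it through.** **Stated figure.** There is none to reproduce. The documents give no significance level, effect size, SD or within-patient correlation for this analysis.

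**Inputs from the documents.** n = 20 patients (Section 12.2); k = 3 stool visits (Section 9.1).

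**Assumed inputs.** Two-sided 5% level; compound symmetry with total variance 1 and within-patient correlation ρ = 0, 0.3, 0.5 or 0.7; complete samples; a shift of 0.5 SD (or 0.8 SD) at end of treatment only.

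**Step 1: error terms.** The expected residual mean square is 1 for the one-way ANOVA and 1 − ρ for the within-patient test. The ratio is 1/(1 − ρ), that is 1.00, 1.43, 2.00 and 3.33 at the four correlations.

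**Step 2: within-patient test with categorical time.** Power comes from a noncentral F with k − 1 and (k − 1)(n − 1) degrees of freedom, here 2 and 38, and λ = n·Σ(μj − μ̄)²/(1 − ρ). For means (0, −0.5, 0), μ̄ = −1/6 and Σ(μj − μ̄)² = 1/36 + 4/36 + 1/36 = 1/6. At ρ = 0.5, λ = 20 × (1/6)/0.5 = 6.67 and power is 59.6%.

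**Step 3: one-way ANOVA.** By simulation, 40,000 runs per setting, with the F test on 2 and 57 degrees of freedom.

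| ρ | ANOVA type I error | Power, 0.5 SD: ANOVA vs within-patient | Power, 0.8 SD: ANOVA vs within-patient |
|---|---|---|---|
| 0 | 5.0% | 34 vs 33% | 72 vs 71% |
| 0.3 | 1.6% | 28 vs 45% | 74 vs 86% |
| 0.5 | 0.4% | 24 vs 60% | 75 vs 95% |
| 0.7 | below 0.1% | 18 vs 83% | 78 vs 99.8% |

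Simulated figures are good to about 1 percentage point.

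**Step 4: other sample sizes** (0.5 SD, ρ = 0.5).

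- 25 patients, three visits: 33 vs 71%.
- 15 patients giving all samples (assumed), three visits: 15 vs 46%.
- 20 patients, four visits: 19 vs 59%.

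**Step 5: coding of time in the mixed model** (20 patients, three visits, 0.5 SD, ρ = 0.5).

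- Categorical time: 60%.
- Natural spline with one interior knot at the middle visit, nominal visit times: three parameters for three time points, so it spans the same space as categorical time; 60%.
- The same spline on variable actual times (assumed 0.4–0.8 and 3.6–6.6 months): 29%.
- Linear time only: 4% with equally spaced visits, or 14% with assumed months 0, 0.6 and 5.1. Both are below the ANOVA's 24%.
- Linear time only, if the shift persists to follow-up: 58% or 28% on the same two time scales, against 60% for categorical time.

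**The case against.** The strongest reply is that Section 12.3 already contains the remedy. A reader who stops at the ANOVA sentence might infer that alpha diversity is analysed only by a test that ignores the pairing. The documents do not support that: the mixed model is extended to the ecology indices. What stands is narrower. The ANOVA remains a stated test, it is the only one tied to alpha diversity by name, and nothing makes the mixed model govern.

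A reader might also infer that the planned mixed model would fail, since a linear time term largely misses a shift confined to end of treatment. That goes too far. The plan provides natural splines for nonlinear trend, and at three nominal visits a spline with a middle knot matches categorical time. The fair statement is that the coding of time, the knots, the rule for using splines and the random-effects structure are left open, so the planned model may or may not recover the loss.

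Nor should the wrong error term be read as a source of spurious findings. With complete data and positive correlation, the ANOVA's type I error falls below 5%.

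Finally, the size depends on assumed values. There is no loss at correlation 0, and at 0.8 SD the ANOVA still has 72–78% power with three visits. Complete data is also optimistic, since the last stool sample is optional. These limits are accepted.

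**Conclusion.** The point holds, as a minor one. Section 12.3 gives two analyses for one question, does not rank them, and one uses the wrong error term for repeated samples. With positive within-patient correlation the one-way ANOVA is conservative and usually loses power.

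For 20 patients, three complete visits and a 0.5 SD shift at end of treatment only, the assumed values put the loss at about 17 percentage points at correlation 0.3 (28 vs 45%), 36 at 0.5 (24 vs 60%) and 65 at 0.7 (18 vs 83%). It is smaller at 0.8 SD and absent at correlation 0. That an ordinary one-way ANOVA has the wrong error term follows from the design and needs none of these assumptions when within-patient correlation is not zero. How much is lost in practice cannot be known from the documents.

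The analysis is exploratory, and the primary safety conclusion is unaffected.

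**What to change.** In Section 12.3, delete the one-way ANOVA or label it descriptive. State that the already planned linear mixed model is the test for each alpha diversity index, with a random intercept per patient and time as a categorical factor with one level per planned stool visit. Categorical time fits the visit-to-visit comparisons in Hypothesis 3, needs no knot choice, and does not depend on the exact day of sampling. The mixed model also keeps patients who did not give every sample.

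Before fixing the number of levels, reconcile Section 9.1 with the Section 5 calendar. Section 9.1 lists three stool time points. The calendar row "Blood draw and microbiome sample" is marked for the post-treatment visits, and its footnote says only "no blood draw at 9-12 months", which read literally leaves a fourth stool sample at 9–12 months.

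The cost is one or two sentences in Section 12.3 and one clarified footnote. No further data or staff are needed.

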We hypothesize that prostate SBRT will be well-tolerated in metastatic prostate cancer patients, with quality of life outcomes similar to what has been reported in non-metastatic prostate cancer patients.

We also hypothesize that prostate SBRT will impact lymphocyte counts and neutrophil

lymphocyte ratio, as well as the diversity, abundance and composition of the gut microbiome, when baseline datapoints are compared to post-RT and follow up datapoints.

Primary objective: To assess safety of delivering MRI-guided prostate SBRT in patients with metastatic prostate cancer.

Treatment will be deemed safe if there is no more than 3 acute >G3 likely radiation treatment related GI/GU toxicity within 3-6 months after treatment (CTCAE 5.0 criteria) completion. Given that the treatment plans will meet rigorous normal tissue constraints used for standard prostate SBRT that have been established now with up to 10 year follow up data in patients with localized prostate cancer, we do not anticipate any increased toxicity on this study for metastatic prostate cancer patients.

Secondary objective: To obtain quality of life and toxicity data after prostate SBRT.

We will measure quality of life (HRQOL) using: 1) the Expanded Prostate Cancer Index Composite (EPIC-26) short form questionnaire, 2) International Prostate Symptom Score (I-PSS). QOL assessments will occur at baseline, 3-6 months, and at 9-12 months.

Toxicity data will be measured with CTCAE 5.0 at 3-6 months, and at 9-12 months.

Correlative study objectives:

1. To explore gut microbiome changes associated with prostate radiation
2. To collect complete blood count (CBC) measurements at baseline, post-treatment and 3-6 month followup to assess impact of SBRT on immune correlates and neutrophil lymphocyte ratios.

SCHEMA

[figure not shown]

TABLE OF CONTENTS

SCHEMA.....	11
1 STUDY OBJECTIVES	14
1.1 PRIMARY OBJECTIVES	14
1.2 SECONDARY OBJECTIVES	14
1.3 CORRELATIVE STUDY OBJECTIVES.....	14
2 BACKGROUND	15
2.1 RADIATION TO THE PROSTATE: RATIONALE FOR TREATING PATIENTS WITH METASTATIC PROSTATE CANCER	15
2.2 PROSTATE CANCER RADIOTHERAPY: RATIONALE FOR EXTREME HYPOFRACTIONATION SBRT	16
2.3 BIOLOGICAL RATIONALE FOR SBRT	16
2.4 SBRT OUTCOMES.....	17
2.5 RATIONALE FOR SIMULTANEOUS INTEGRATED BOOST.....	18
2.6 NEED FOR IGRT IN PROSTATE RADIOTHERAPY.....	18
2.7 VIEWRAY: A UNIQUE RADIATION DELIVERY APPROACH	19
2.8 RATIONALE FOR CORRELATIVE STUDIES BACKGROUND: MICROBIOME AND BLOOD SAMPLE COLLECTION	20

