1 STUDY OBJECTIVES

HYPOTHESIS 1: Patients with metastatic prostate cancer can undergo MRI-guided prostate SBRT w/SIB without significant adverse events, similar to what has been reported for patients with localized prostate cancer using CTCAE criteria.

HYPOTHESIS 2: Patients with metastatic prostate cancer who undergo MRI-guided prostate SBRT will report good overall quality of life, similar to what has been reported for patients with localized prostate cancer. This will be measured using EPIC-26, I-PSS questionnaires, which are validated instruments that have been used to report QOL outcomes after prostate RT.

HYPOTHESIS 3: Patients may experience decline in neutrophil:lymphocyte ratios during radiation therapy, that is most prominent at end of treatment, but recovers to baseline by follow up. There will be alterations in the composition, diversity and abundance of microflora during radiation therapy when the microbiome is compared at baseline, to post-treatment, to follow up.

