1.3 Correlative Study Objectives

1.31

To collect complete blood count (CBC) measurements at baseline, post-treatment and 3-6 month followup to assess impact of SBRT on immune correlates and neutrophil lymphocyte ratios.

To describe gut microbiome changes (abundance, composition, diversity) associated with prostate radiation.

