3.3 Exclusion Criteria

1. History of prior pelvic radiation (external beam or brachytherapy)
2. Inability to undergo MRI
3. AUA score >20
5. For patients on systemic therapy, enrollment must be within six months of start of therapy unless exception is made by protocol PIs (Drs. [name], [name] or [name])

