Plasma samples will be collected at three time points: before radiation, following completion, and 3-6 months after completion. We hope to understand the impact of radiation on the distribution and frequency of peripheral immune mediators at these time points. To this effect, NLR will be numerically and graphically summarized in several ways. The average ratio at each time will be estimated, as well as average changes from baseline, and individual trajectories will be plotted in “spaghetti plots.” Parallel summaries will be presented dichotomizing N/L ratio at 4%, counting the proportion of patients above this threshold at each time point.

Several markers beyond N/L ratio are of interest in order to thoroughly characterize changes throughout radiation treatment, including continuous (e.g. T cell panel and TREG panel, IL-7, IL-15, IL-6, IL-10, IL-17, IL-2 cytokines), and categorical (e.g. proliferative ability) measures. These will be summarized and analyzed in an exploratory manner in parallel methods to N/L ratio, if funding is secured for these analyses.

13 Data and Safety Monitoring Plan (DSMP)

The WCMC Data and Safety Monitoring Committee (DSMC) is the central monitoring board for this study.

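### The Protocol Summary hypothesizes an effect on lymphocyte counts, but the only unconditional blood analysis in Section 12.3 is NLR, which cannot by itself show whether lymphocytes fell

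*Combined protocol and SAP*

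**What the plan says.** The blood correlates are described in several places, and they do not all name the same outcome.

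- **Protocol Summary, hypotheses:** "We also hypothesize that prostate SBRT will impact lymphocyte counts and neutrophil" (the sentence goes on to the lymphocyte ratio and the gut microbiome). Counts and ratio are listed as two things, each compared between baseline, post-RT and follow-up.
- **Section 2.8:** the site's preliminary results are said to "demonstrate depletion of circulating lymphocytes in prostate cancer patients undergoing protracted standard radiation compared to 5-fraction SBRT", followed by "We will study this phenomenon further in patients undergoing SBRT on this study". NLR is then introduced as a further finding, a temporary increase during prostate radiation.
- **Section 1, Hypothesis 3:** "Patients may experience decline in neutrophil:lymphocyte ratios during radiation therapy". For blood, this names NLR only.
- **Section 1.3:** "To collect complete blood count (CBC) measurements at baseline, post-treatment and 3-6 month followup to assess impact of SBRT on immune correlates" and NLR.
- **Section 9.1:** anticipates T-cell subsets, NLR, cytokines and proliferation. It does not name an absolute lymphocyte count.
- **Section 12.3, CBC collection:** "To this effect, NLR will be numerically and graphically summarized in several ways". The summaries are the mean at each time, the mean change from baseline, individual trajectories, and the proportion above a cut-off written as 4%. A second paragraph lists T-cell and Treg panels, cytokines and proliferative ability, to be handled in the same way provided funding is obtained.

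**The concern.** A hypothesis about lymphocyte counts needs an analysis of lymphocyte counts. Section 12.3 commits without condition only to a ratio in which the lymphocyte count is the denominator. A change in that ratio can come from either cell line, and opposite or parallel movements can exaggerate it or cancel it.

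Two features of the protocol make the ratio harder to read alone. The documents disagree on its expected direction: Hypothesis 3 expects a decline, while Section 2.8 reports a temporary increase. And neutrophils cannot simply be taken as constant between samples. There is no control arm, and some patients may have begun other treatment recently: "For patients on systemic therapy, enrollment must be within six months of start of therapy", with exceptions allowed.

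At stake is whether the trial can answer this correlative question. A rise in NLR might be reported as radiation lymphopenia when neutrophils had risen, or a real lymphocyte loss might leave the ratio flat and go unreported.

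**Working it through.** **No stated figure to reproduce.** The documents give no sample size, power, effect size or standard deviation for the blood endpoints. The check is therefore a comparison of hypothesis with analysis, then arithmetic on the ratio.

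**Step 1. Match outcomes to analyses.**

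| Blood outcome | Where it is hypothesized or promised | Analysis in Section 12.3 |
|---|---|---|
| NLR | Protocol Summary, Hypothesis 3, Sections 1.3 and 2.8 | Mean, change, trajectories, dichotomy; unconditional |
| Lymphocyte count | Protocol Summary; depletion in Section 2.8 | Not named |
| T-cell and Treg panels, cytokines, proliferation | Section 9.1 | Parallel summaries, only if funded |

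**Step 2. What NLR identifies.** Let N and L be the two counts, and n and l their proportional changes. Then

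NLR after / NLR before = (1 + n) / (1 + l).

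This is one equation with two unknowns. For any observed NLR change, every value of l is compatible with some value of n.

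**Step 3. Illustration.** The baseline counts are assumed, not taken from the documents: N = 4.0 and L = 1.6 (×10^9/L), so NLR = 4.0/1.6 = 2.5.

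| Scenario | N | L | NLR | Lymphocyte change |
|---|---|---|---|---|
| L falls 40%, N unchanged | 4.0 | 1.6 × 0.6 = 0.96 | 4.0/0.96 = 4.17 | −40% |
| N rises about 67%, L unchanged | 6.67 | 1.6 | 6.67/1.6 = 4.17 | none |
| Both fall 40% | 4.0 × 0.6 = 2.4 | 0.96 | 2.4/0.96 = 2.5 | −40% |
| L falls 50%, N falls 60% | 4.0 × 0.4 = 1.6 | 1.6 × 0.5 = 0.8 | 1.6/0.8 = 2.0 | −50% |

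The first two rows have the same NLR and different lymphocyte outcomes. The first and third have the same lymphocyte loss and different NLRs. In the fourth, NLR declines, as Hypothesis 3 expects, while lymphocytes halve. If the cut-off written as 4% means a ratio of 4, the planned dichotomy flags the first two rows alike and misses the third.

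Other baseline counts change the absolute values but not the result, because the formula in Step 2 involves only the proportional changes.

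**Step 4. Precision if the count is added.** The 95% confidence interval for a mean paired change has half-width t(0.975, m − 1)/√m, in units of the standard deviation of the change, where m is the number of pairs.

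- m = 20 (planned sample size): 0.468 SD
- m = 25 (accrual ceiling): 0.413 SD
- m = 15: 0.554 SD
- m = 10: 0.715 SD

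The last two values of m are assumptions to allow for missing samples. The documents do not give the standard deviation, so the widths cannot be turned into cell counts.

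**The case against.** The strongest reply is that Section 12.3 follows the formal statement of the study. Hypothesis 3 names only NLR for blood, and Section 1.3 names immune correlates and NLR, not lymphocyte counts. On that view the stray text is the clause in the Protocol Summary. This stands in part: the gap lies between the summary and Section 1 as well as between the summary and Section 12.3. It does not withdraw the summary's hypothesis or the commitment in Section 2.8, so the passages need to be aligned.

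A second reply is that these analyses are exploratory, with no test or decision rule, and nothing stops the team from reporting the counts. That is a fair limit on importance. But exploratory status excuses low precision, not leaving out a hypothesized variable.

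Four stronger readings might be inferred, and the documents do not support them.

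- **That nothing but NLR is planned for blood.** Section 12.3 lists T-cell and Treg panels, which are lymphocyte measures, and Section 9.1 anticipates T-cell subsets without repeating the funding condition. But Section 12.3 makes these panels conditional, and subsets are not the total count.
- **That Section 2.8 reports lymphocyte depletion from SBRT, or that this trial could confirm its finding.** The depletion described is in protracted radiation compared with five-fraction SBRT. A single-arm SBRT study cannot reproduce that contrast, with or without the count.
- **That a CBC with differential is stated.** The text says CBC only. The differential is an inference from the planned NLR, which cannot be calculated without it.
- **That results must be split by systemic therapy or steroid use.** Steroids are not mentioned, and such a split of about 20 patients would leave very small descriptive cells.

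**Conclusion.** The point holds in a limited form. A hypothesis about lymphocyte counts is stated, no analysis of the count is specified, and the one unconditional blood analysis cannot stand in for it. That NLR alone does not determine the lymphocyte change is algebra and needs no assumption. The figures of 2.5 and about 4.2 rest on assumed counts and only illustrate it. No document figure says how often neutrophils and lymphocytes would move together in these patients, so the chance of a misleading NLR result cannot be estimated.

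The consequence is confined to an exploratory correlative question. The primary safety conclusion and the quality-of-life analyses are untouched. The change is still worth making, because without it a stated hypothesis goes unanswered.

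**What to change.** In Section 12.3, CBC collection:

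1. Name absolute lymphocyte count and absolute neutrophil count as CBC endpoints at baseline, completion of radiation and 3-6 months.
2. Summarize each as NLR is summarized, with mean and median, paired change from baseline with a 95% confidence interval, and individual trajectories. Give the number of pairs at each time.
3. State that any change in NLR will be interpreted alongside the two counts.
4. Align the blood hypothesis in the Protocol Summary with Hypothesis 3 so that both name the same outcomes.

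The cost is a few more descriptive rows and plots. The counts come from the same CBC and differential that NLR requires, so no additional draw or funded assay should be needed, provided the differential was recorded. The version 5.0 summary of changes says the study is closed to accrual and in follow-up; this does not block a change that concerns analysis only. No subgroup table by systemic therapy or steroid use is needed.
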